### 5.2.1. Rationale for Duration between Therapies

As part of the study design, subjects must receive their first dose of daclizumab at 28 (+ 3) days following discontinuation of natalizumab. The rationale for this requirement is to minimize the washout period between daclizumab and natalizumab. Clinical research studies in patients switching from natalizumab to an alternative treatment option have shown that disease activity can occur within the first 6 months of discontinuing natalizumab. However, in several of these studies, the risk of disease recurrence was shown to be mitigated with a shorter washout period between treatments [Cohan 2015; Kappos 2015c]. In a randomized trial evaluating the effects of natalizumab treatment interruption (RESTORE), it was shown that natalizumab concentrations reach undetectable levels 8 weeks after discontinuation [Cree 2013]. Pharmacodynamic (PD) studies with daclizumab demonstrated increases in CD56bright NK cells and serum IL-2 levels within the first 4 weeks of treatment [Amaravadi 2015] and effects on disease activity, as evidenced by reductions in Gd+ lesion activity, were apparent within 8 to 12 weeks (SELECT; Biogen, data on file). These data indicate that a 28-day gap between the discontinuation of natalizumab and the initiation of daclizumab would maximize the PD overlap of these 2 therapies and thus minimize the amount of time patients are not protected by a highly efficacious therapy.

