## **13. STATISTICAL CONSIDERATIONS**

### **13.1. Sample Size Justification**

This study will enroll approximately 100 subjects. The sample size is estimated based on the proportion of subjects who are relapse-free at Month 6.

Assuming a drop-out rate of 10%, the evaluable sample size will be 90. A two-sided 95% confidence interval (CI) for a single proportion of subjects on daclizumab 150 mg remaining free of relapses at the end of Month 6 will extend between 8.3% and 6.7% from the observed proportion for an expected proportion of 80% to 88%, respectively.

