2 STUDY DESIGN AND SAMPLE SIZE

This is a multicenter, open-label study of daclizumab monotherapy in subjects with RRMS who were previously treated with natalizumab for at least 12 months. Subjects will be enrolled over an approximately 12-month period. Subjects discontinuing from natalizumab treatment due to safety concerns will commence treatment with daclizumab beta following consent and evaluation of eligibility. Subjects will initiate treatment with daclizumab beta at 28 (+3) days following the last infusion of natalizumab. Assessments will be completed at enrollment, baseline, Month 1, Month 3, Month 4, Month 6, Month 9 and Month 12.

The duration of subject participation will be up to 16 months, including a 28 (+3) day screening period, treatment with daclizumab beta for up to 12 months, and an additional safety follow-up visit performed remotely 4 months after last study treatment dose. Subjects having tentative disability progression near the end of the core study (e.g., Month 12) will attend additional follow-up visits 12 and 24 weeks later to confirm progression. This study will enroll approximately 100 subjects. The sample size is estimated based on the proportion of subjects who are relapse-free at Month 6.

On March 2, 2018, daclizumab beta has been voluntarily withdrawn from the global market and the drug supply to patients has been stopped. As a result SUSTAIN has been terminated. An abbreviated clinical study report will be developed based on the patient data available upon the withdrawal and from the safety follow-up.

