4 GENERAL CONSIDERATIONS

The SUSTAIN study was terminated early by sponsor upon the withdrawal of daclizumab from the global market after approximately 30 subjects were enrolled in study. Because the study was not fully enrolled and there was limited follow-up time, some endpoints will no longer be analyzed and some endpoints and outcomes will be summarized in listings rather than data tabulations. Missing data in this study will not be imputed.

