4.6 General Information on Statistical Analysis

Summary statistics will be generated for all efficacy, safety, PK/PD parameters, demographic/baseline variables and other variables where applicable. For the continuous endpoints, the summary statistics will generally include number of subjects, mean, standard deviation, median, 25th and 75th percentile, minimum and maximum. For categorical endpoints, the summary statistics will generally include number of subjects in corresponding analysis population, number and the percentage of subjects in each category.

In general, all efficacy endpoint analyses where applicable will include the baseline covariates; the covariates included in the statistical models for efficacy endpoints are selected to be consistent with analysis models in other previously reported Phase 3 MS studies.

All statistical tests will be 2-sided with an overall type I error rate of 0.05; no multiple testing adjustment will be performed in this study.

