5.2.2 Analysis for Annualized Relapse Rate (ARR)

ARR will be analyzed for both treatment period and study period. Please see section 4.1 for their definitions.

The number of relapses observed during the treatment period (or during the study period) will be summarized as a categorical variable (number of relapse being 0, 1, 2, 3 and ≥ 4).

The unadjusted relapse rate will be calculated as the total number of relapses observed divided by the total number of days on treatment (or on study) multiplied by 365.25.

If there is sufficient data, the adjusted mean annualized relapse rate and its 95% confidence interval (CI) during the treatment period will be estimated by a negative binomial model; proper covariates are adjusted in the model. The logarithmic transformation of the number of days in the study will be included in the model as the “offset” parameter. If the data is under-dispersed or if the negative binomial regression model does not converge, a Poisson model will be used instead of the negative binomial regression model. Dispersion will be evaluated from the Pearson Chi-Square statistic. If the ratio of the Pearson Chi-Square statistic to the degrees of freedom is < 1 then a Poisson regression model will be used.

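### SAP 5.2.2 gives the crude annualized relapse rate no confidence interval; its only ARR interval is conditional and rests on a covariate-adjusted mean whose covariates and averaging are not stated

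*SAP*

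**What the plan says.** ARR at Month 12 is a secondary endpoint (SAP 1.2). SAP 5.2.2 provides two estimates.

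- **Crude rate.** "The unadjusted relapse rate will be calculated as the total number of relapses observed divided by the total number of days on treatment", scaled by 365.25, and likewise for the study period. It is unconditional and covers both periods. No interval is mentioned.
- **Adjusted mean.** The adjusted mean ARR and its 95% interval "will be estimated by a negative binomial model; proper covariates are adjusted in the model", with a Poisson model if the data are under-dispersed or the fit fails. This applies to the treatment period only, and only if the data are sufficient. No criterion for sufficiency is given. The offset is the log of days in the study.

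SAP 4.6 adds that "all efficacy endpoint analyses where applicable will include the baseline covariates". It says they are chosen to agree with models in previously reported Phase 3 MS studies, but neither names nor counts them. Neither section says whether the adjusted mean is taken at the covariate means or averaged over subjects.

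Protocol 13.5.1 describes ARR as total relapses over total person-years, to be given with a 95% interval from a negative binomial model. It sets no sufficiency condition. The SAP was written after termination, "after approximately 30 subjects were enrolled in study".

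**The concern.** The design is a single arm: "This is a multicenter, open-label study of daclizumab monotherapy in subjects with RRMS". In a randomised trial, covariates sharpen a treatment contrast. Here there is none, and the target is one rate in one group. With a log link, the rate at average covariates is not the average rate. It is lower, and fitting several covariates to few relapses lowers it further.

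Two things are at stake. If the data are judged insufficient, a listed secondary endpoint is reported with no measure of uncertainty. If they are judged sufficient, the only interval may sit on a number that differs from the crude rate for reasons unrelated to the drug. Readers may set the result beside rates in the protocol's own background: 0.22 on daclizumab in the active-controlled Phase 3 trial, and 0.248 after switching from natalizumab to dimethyl fumarate. A shift of a few tenths of the rate would alter that impression.

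**Working it through.** **The plan's own precision figure.** The documents give one, for the primary endpoint: "Assuming a drop-out rate of 10%, the evaluable sample size will be 90", with half-widths of 8.3% and 6.7% at 80% and 88%. The Wald formula 1.96 × √(p(1−p)/90) gives 8.26% and 6.71%, so it reproduces. No precision figure is given for ARR.

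**Inputs.** From the SAP: about 30 subjects, one arm, a log-link model, and two-sided 95% intervals ("All statistical tests will be 2-sided with an overall type I error rate of 0.05"). Assumed, because the documents give no figure: mean follow-up of 0.5 or 0.9 years, true ARR of 0.2 or 0.4, 1 to 4 standard normal covariates, log rate ratio of 0 or 0.3 per SD, gamma dispersion of 0.5. Expected relapses are 30 × follow-up × ARR, i.e. 3.0, 5.4, 6.0 and 10.8.

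**Direction.** The rate at the covariate means is exp(mean of Xb). The average rate is the mean of exp(Xb), which is never smaller. For normal covariates the ratio is exp(−variance/2). One covariate at 0.3 gives exp(−0.045) = 0.96, and three give exp(−0.135) = 0.87. Simulation at n = 1000 gave 0.95 and 0.87.

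**Size at n = 30.** There were 250 runs per setting, each a negative binomial fit with the SAP's switch to Poisson when Pearson/df is below 1. Runs with no relapse were left out. Entries are the mean rate at covariate means divided by the mean crude rate, for log rate ratio 0 / 0.3.

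| True ARR, mean follow-up | 1 covariate | 2 | 3 | 4 |
|---|---|---|---|---|
| 0.2, 0.5 y | 0.86 / 0.82 | 0.71 / 0.68 | 0.58 / 0.54 | 0.48 / 0.40 |
| 0.2, 0.9 y | 0.89 / 0.88 | 0.84 / 0.77 | 0.75 / 0.64 | 0.63 / 0.53 |
| 0.4, 0.5 y | 0.93 / 0.89 | 0.83 / 0.76 | 0.78 / 0.66 | 0.67 / 0.55 |
| 0.4, 0.9 y | 0.94 / 0.90 | 0.90 / 0.83 | 0.84 / 0.75 | 0.79 / 0.64 |

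The shortfall is therefore 6% to 18% with one covariate and 10% to 60% with two to four. Much of it is overfitting, since it appears even when the covariates have no effect. With no covariates (Poisson fit) the ratio is 1.00.

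**The other reading.** Averaging the same fits over subjects gave medians of 0.19 to 0.21 for true 0.2, and 0.36 to 0.41 for true 0.4. For the Poisson model this is nearly an identity. The score equation for the intercept forces fitted relapses to sum to observed relapses, so the exposure-weighted average prediction equals the crude rate.

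**Exact Poisson interval for the crude rate.** For d relapses in T person-years, the lower limit is χ²(0.025; 2d)/(2T) and the upper limit is χ²(0.975; 2d+2)/(2T). Illustrative counts:

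- 3 in 15: 0.20 (0.04 to 0.58)
- 6 in 30: 0.20 (0.07 to 0.44)
- 6 in 15: 0.40 (0.15 to 0.87)
- 12 in 30: 0.40 (0.21 to 0.70)

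In a separate simulation (n = 30, Poisson counts, follow-up of 1 to 12 months, ARR 0.22) this interval covered the truth about 97% to 98% of the time.

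**Offset.** SAP 4.1 ends the treatment period at the last dose and the study period at the last visit. The model concerns the treatment period, but its offset is days in the study. Read literally, treatment-period relapses over study days scale the rate by treatment days/study days. With assumed day counts, 335/365 = 0.92 and 335/455 = 0.74.

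**The case against.** A reader might infer that the SAP's model pulls ARR well below the truth and so favours the drug by construction. The documents do not support that. It requires evaluation at the covariate means and several covariates, and the SAP fixes neither. Averaging over subjects removes almost all of the shortfall.

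The sufficiency condition should also stop the model in the worst cases, those with about 3 relapses and 4 covariates. That is fair, but without a threshold nobody can say when it applies, and when it does apply ARR is left with no interval.

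The crude rate is already planned for both periods, so a low adjusted value would appear beside it. No test against 0.22 or 0.248 is planned, and that comparison is only one a reader might make. Both points stand, but a bare 0.20 without its interval would still look more precise than it is.

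The SAP also follows the protocol, which itself foresaw a negative binomial model and mentioned covariates. That too is correct, but the protocol planned for about 100 subjects and set no condition on the interval.

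Finally, a reader might infer from Protocol 5.2.1 that risk concentrates early, so that one pooled rate misleads. The text says only that "disease activity can occur within the first 6 months of discontinuing natalizumab". That is a possibility, and it is timed from stopping natalizumab, not from the first daclizumab dose. A split into Months 0–6 and 6–12 is optional and no part of the error.

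**Conclusion.** The point holds in limited form. The following is certain from the text:

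- The crude ARR has no interval in either period.
- The only ARR interval is conditional, treatment-period only, and attached to an adjusted mean with unnamed covariates and no stated way of averaging.
- The offset does not match the period modelled.

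The possible shortfall (6% to 18% with one covariate, 10% to 60% with two to four, near zero if averaged over subjects) rests on the assumed relapse counts, follow-up and covariate strength. It shows what the wording permits and does not predict the result.

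This should be fixed as a cheap improvement. It is not critical, because it concerns a conditional estimate of a secondary endpoint in a terminated study, and the primary analysis does not use it.

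**What to change.** In SAP 5.2.2:

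1. Make the crude ARR with an exact Poisson 95% interval the main ARR result for both the treatment and study periods, showing relapses and person-years. This needs no sufficiency condition and works even with no relapses.
2. Drop the covariates. If a model is kept, fit it intercept-only, with an offset equal to the time in the period analysed: treatment days for treatment-period relapses, study days for study-period relapses.
3. If covariates are kept, name them, state that the adjusted mean averages predictions over subjects, and give a threshold for sufficient data.

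The cost is a few lines of SAP text and simpler programming. The drawback is that the exact Poisson interval ignores clustering of relapses within subjects. The table of 0, 1, 2, 3 and ≥ 4 relapses that the SAP already plans would show any such clustering.

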### **7.2. Overall Study Duration and Follow-Up**

The study will consist of a 28-day (+3 days) screening period for each subject, a 12-month treatment period, and a 4-month remote safety follow-up visit after the subject's last treatment injection. The end of the study for each subject will be the last study visit or the visit at which the subject discontinues from the study (before the 12-month visit). Each follow-up visit will include a 4-day window before and after the visit for completion of all assessments. The follow-up period will include efficacy and safety following treatment initiation of daclizumab. The end of the study overall will be defined as the end of the 12-month study follow-up period for the last patient. The 4-month safety follow-up visit will be conducted remotely after the 12-month study follow-up visits have been completed.

Subjects having tentative disability progression identified near the end of the core study (e.g., Month 12) will attend additional follow-up visits 12 and 24 weeks later to confirm progression.

Subjects may discontinue treatment at any time during the study, and they will be followed for an additional 4 months to collect data on safety, LFT, MS treatment, relapses, and the use of concomitant medications.

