4.1 Treatment Period Definitions

Based on the schedule of assessment, we have the following definitions:

- **the first dosing date** is the date when the subject is first dosed;
- **the last dosing date** is the date of the last date the subject is dosed;
- **The end of study date** is the last visit date;

- **Treatment period, or, time on (study) treatment**, is defined as the time between the first dosing date and the last dosing date; it is calculated as the last dosing date minus the first dosing date + 1; also known as the time exposed to study drug;
- **Time on study, or study period**, is defined as the time between the first dosing date and the end of study date, calculated as the last visit date – the first dosing date + 1.

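### SAP 5.2.2 models the treatment-period relapse rate with study days as the offset, so the adjusted ARR and its CI come out too low if treatment-period relapses are counted

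*SAP*

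**What the plan says.** SAP section 5.2.2 plans the ARR for both the treatment period and the study period and refers to section 4.1 for the definitions. There, time on treatment "is defined as the time between the first dosing date and the last dosing date", and time on study "is defined as the time between the first dosing date and the end of study date". The end of study date is the last visit date.

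The unadjusted rate in 5.2.2 keeps the two apart. Its denominator follows the period: relapses are "divided by the total number of days on treatment (or on study) multiplied by 365.25".

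The model-based rate does not. If the data suffice, "the adjusted mean annualized relapse rate and its 95% confidence interval (CI) during the treatment period will be estimated by a negative binomial model". The offset sentence then reads: "The logarithmic transformation of the number of days in the study will be included in the model". Nothing in the section switches the offset to treatment days or says that this model counts study-period relapses.

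Protocol section 13.5.1 defines the ARR differently again: relapses over person-years in the study up to Month 12, also by a negative binomial model.

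**The concern.** In a log-link count model the offset is the person-time over which the events were counted. Followed literally, 5.2.2 puts relapses from the shorter window (first to last dose) over time from the longer one (first dose to last visit). Days after the last dose then add to the denominator while relapses on those days are left out of the numerator. The rate can only fall, and that favours the drug.

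The ARR is a named secondary endpoint, and this model is the only place in 5.2.2 that gives it a confidence interval. The same report would also carry an unadjusted treatment-period ARR with matched person-time. The two would disagree for a reason that has nothing to do with covariate adjustment.

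How much extra time enters depends on what counts as the last visit, which the documents leave open. Protocol Table 1 numbers the safety follow-up as Visit 9 and schedules a relapse assessment there. SAP section 2 says the report will be "based on the patient data available upon the withdrawal and from the safety follow-up". Against that, protocol section 7.2 ends the study overall at the 12-month follow-up and says: "The 4-month safety follow-up visit will be conducted remotely after the 12-month study follow-up visits have been completed".

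**Working it through.** The documents give no ARR, event count or precision that depends on this offset, so there is no plan figure to reproduce. The check is on the size of the distortion if treatment-period relapses are counted.

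**Inputs**
- Treatment days and study days: as defined in SAP 4.1.
- Dosing: monthly from baseline to Month 11 (protocol Table 1, footnote 8), so at most 12 doses.
- Safety contact: 4 months after the last dose (SAP section 2).
- Month 12 visit: one month after a Month 11 dose.
- Illustrative true rate: 0.22 per year, the daclizumab ARR quoted in protocol section 5.1.4 from the active-controlled trial. It is not a design value of this study.
- Assumed: mean number of doses *k*, and a fixed gap *g* from last dose to last visit. Months are about 30.44 days.

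**Formulas**
- Treatment days: T = (k − 1) × 30.44 + 1.
- Study days: S = T + g, with g = 30.44 (one month) or 121.75 (4 months).
- For an intercept-only Poisson model the fitted rate is total relapses / total offset time. Using S in place of T therefore multiplies the rate by ΣT/ΣS = mean T / (mean T + g). With a fixed gap this depends only on the mean number of doses.

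**Results**

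| Mean doses | T (days) | Factor, 1-month gap | Too low by | Factor, 4-month gap | Too low by |
|---|---|---|---|---|---|
| 12 | 335.8 | 335.8/366.3 = 0.92 | 8% | 335.8/457.6 = 0.73 | 27% |
| 9 | 244.5 | 244.5/275.0 = 0.89 | 11% | 244.5/366.3 = 0.67 | 33% |
| 6 | 153.2 | 153.2/183.6 = 0.83 | 17% | 153.2/275.0 = 0.56 | 44% |
| 3 | 61.9 | 61.9/92.3 = 0.67 | 33% | 61.9/183.6 = 0.34 | 66% |

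At a mean of 6 doses, a true on-treatment ARR of 0.22 would be reported as 0.22 × 0.83 = 0.18 (1-month gap) or 0.22 × 0.56 = 0.12 (4-month gap).

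**Does the factor carry over to the negative binomial model?** Intercept-only fits to 200,000 simulated subjects (true rate 0.22, dispersion 1) gave these ratios of the rate with offset log S to the rate with offset log T:

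| Doses, uniform over | 4-month gap: fitted ratio (ΣT/ΣS) | 1-month gap: fitted ratio (ΣT/ΣS) |
|---|---|---|
| 1–12 | 0.575 (0.580) | 0.843 (0.847) |
| 3–9 | 0.555 (0.557) | 0.833 (0.834) |
| 6–12 | 0.666 (0.668) | 0.889 (0.889) |
| 1–5 | 0.335 (0.337) | 0.667 (0.670) |

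**Does the interval move too?** Yes.
- 3,000 simulated subjects, 2 to 12 doses, 4-month gap: the negative binomial estimate went from 0.223 (95% CI 0.199 to 0.250) to 0.133 (0.119 to 0.149).
- T/S fixed at 336/366 for everyone: the estimate and both limits were multiplied by 0.918.

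Covariate adjustment was not simulated.

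**The case against.** The strongest reply is that the offset is right and the label is wrong. Protocol 13.5.1 uses person-years in the study, so study days agree with the protocol and the treatment-period phrase is what departs from it. If study-period relapses are counted, there is no bias. This stands as a possible reading. It does not clear the text, because one half of the specification must still change.

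A second reply is that the offset phrase is loose wording and not the defined term for time on study. But 5.2.2 sends the reader to the 4.1 definitions and separates the two periods in the preceding paragraph, so the choice should not fall to the programmer.

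Third, the large factors need every subject's last visit to be the 4-month contact. Protocol 7.2 leans towards the shorter gap, and the protocol's Month 12 cap would hold the 12-dose case near 0.92. That is fair, and the 4-month column is a scenario only. With the one-month gap, the added time is an ordinary dosing interval, so calling it off-drug time would overstate the matter.

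Fourth, SAP 5.1 counts relapses up to the end-of-treatment visit. If the ARR did the same, an offset ending at the last dose would be mismatched in the other direction. That rule is written for the primary analysis, while 5.2.2 points to 4.1. It is still a good reason to state the counting window outright.

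Finally, precision is poor. With about 30 subjects (SAP section 4), if all were dosed with a mean of 6 doses, there are 30 × 153.2/365.25 = 12.6 person-years and 0.22 × 12.6 = 2.8 expected relapses. Three relapses would give exact Poisson limits of about 0.05 to 0.70 per year, so a shift from 0.22 to 0.18 is small beside that, and the model may never be run. This limits the importance of the point. It does not excuse the mismatch: the upper limit shrinks as well, from 0.70 to 0.70 × 0.83 = 0.58 or 0.70 × 0.56 = 0.39.

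**Conclusion.** The point holds. SAP 5.2.2 names one period for the adjusted ARR and takes its person-time from another. With treatment-period relapses, the estimate and its interval are too low by about total treatment days over total study days. That is 8% to 33% for a one-month gap and 27% to 66% for a 4-month gap, over mean exposures of 12 down to 3 doses. Shorter exposure makes it worse, and early termination makes short exposure plausible.

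The direction is certain on that reading, provided last visits fall after last doses. The size rests on assumed dose counts and visit gaps, because actual dates are not in the documents. On the other reading the rate is sound and only the label is wrong.

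This should be fixed, but its reach is limited. The endpoint is secondary, the model is conditional on enough data, the matched unadjusted ARR is reported in any case, and the primary endpoint does not use this offset.

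**What to change.** In SAP 5.2.2, state the relapse-counting window for the model and use log days in that same window as the offset:

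- **Treatment-period ARR:** count relapses from first to last dosing date, with log(days on treatment) as defined in SAP 4.1 as the offset.
- **Study-period ARR, if it is modelled:** count relapses from first dosing date to last visit, with log(days on study) as the offset. Label the result as the study-period ARR and say whether the remote safety contact counts as the last visit.

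The definitions in SAP 4.1 can stay. If the study-period version is meant to be the protocol's ARR, say how it relates to the Month 12 limit in protocol 13.5.1.

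The cost is one line of SAP text and one offset variable in the program. No new data are needed.
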